9.4. Data Sources

This retrospective observational study will be conducted using linked national patient-level data from the VA and Center for Medicare and Medicare Services (CMS) fee-for-service database and Veterans’ Health Affairs database. The study period will be from January 1, 2013 through December 31, 2017. Patients with NVAf diagnosis will first be identified in VA dataset and then linked to Medicare data using social security number (SSN) as a unique patient identifier. Linked patient records will be deidentified before analysis. There will be no duplicate records and all outcomes will be counted only once in the linked database. Once the linked database is created, demographic, clinical, HRU, and cost outcomes will be available from the linked patient records using both Medicare and VA database. There will not be any overlapping HCRU or costs claims since VA is a closed system. If patient uses VA system then we will see a claim from VA database, if they use Medicare, they we will see a claim from Medicare database. So, all the claims will be unique with no overlapping.

In addition, VA data includes vital measures (BMI, body weight, height) and laboratory results (INR, TTR) that are not available in Medicare claims data. Using linked VA and Medicare data provides a more robust patient history as vital measures and laboratory results can be evaluated. BMI, body weight, and height are of importance when stratifying patients in obese and severely obese cohorts and INR and TTR allow evaluation of warfarin management. This study will add to an existing body of literature that evaluates various populations across different disease states the use linked VA and Medicare data to provide a more robust study population.^{27,28}

Veterans’ Health Affairs (VHA) Data

9.4.1. VA Database

The VHA is the largest integrated health care system in the United States, providing care for veterans across the country. According to U.S. Department of Veterans Affairs (VA) estimates, there were approximately 24 million living veterans of the U.S. military in 2006. That year, the department provided medical services to more than five million of those veterans and to more than 400,000 other patients (ie, employees, eligible dependents and survivors of disabled veterans, and patients seen through sharing agreements with other providers such as the Department of Defense's TRICARE program). An additional 2.9 million veterans were enrolled in the system but did not seek services from the department that year, and the VA estimates that 5.8 million eligible veterans were never enrolled.²⁹

The size and structure of the VHA system is quite different from most private care organizations. The system includes:

- 162 VA hospitals;
- 137 nursing homes;
- 43 domiciliaries;
- 850+ community and facility-based clinics;
- 14,800 doctors;
- 61,000 nurses; and
- 5 million patients.³⁰

The system began as a network of hospitals and grew to include more aspects of care including clinics and nursing homes. Twenty-two regional networks, called the Veterans Integrated Service Networks (VISNs) have been created since 1995. Most VISNs consist of 7 to 10 hospitals, 25 to 30 ambulatory care clinics, 4 to 7 nursing homes, and 1 to 2 domiciliaries.³¹

The VHA Medical SAS[®] datasets are national administrative data for VHA-provided health care utilized primarily by veterans, but also by some non-veterans (eg, employees, research participants). The datasets are provided in SAS[®] format by fiscal year (FY) (October 1-September 30). These data are extracted from the National Patient Care Database (NPCD) as maintained by the VHA Office of Information at the Austin Information Technology Center (AITC), the central repository for VA data.

VHA Medical SAS® datasets include four inpatient datasets and two outpatient datasets. Variables common to both inpatient and outpatient data files include demographics (age, sex, race, birth date, marital status, city, county, and state of residence); period of military service; and selected special characteristics, including the patient's spinal cord injury status, prisoner of war history, and radiation or Agent Orange exposure. Also included are the patient's category of eligibility for VHA medical care, and the extent of a service-connected disability.

VHA Medical SAS® Inpatient Datasets

The Medical SAS® Inpatient datasets cover four main categories of care: acute, extended, observation, and non-VA. Within each of these categories there are four datasets:

- **Main:** A patient's inpatient stay (episode of care);
- **Bed Section:** A patient's inpatient stay under a specified physician treating for a specialty service;
- **Procedure:** One day's procedure during an inpatient stay; and
- **Surgery:** One day's surgeries during an inpatient stay.

Inpatient variables describing each hospital admission include date, time, facility, and the primary diagnosis at admission. Discharge data include date, time, destination (eg, home, hospice, community nursing home), type of discharge (eg, regular, transfer to another hospital, death), and length of stay (LOS).

VHA Medical SAS® Outpatient Datasets

Each outpatient data record represents one date of service for one outpatient, and includes a facility identifier, date and time of visit, and the type of clinic location where care was provided. Visits on a single day to multiple clinics, laboratories, and treatment programs are captured.

Outpatient care is reported in terms of diagnoses (International Classification of Diseases, 9th and 10th Revision, Clinical Modification [ICD-9-CM and ICD-10-CM] codes) and procedure (Current Procedural Terminology [CPT] codes), including dates and times. The type of provider for each service is reported using a VHA list of more than 500 categories (these may be changed in the future to agree with provider-type codes used by the Centers for Medicare and Medicaid Services [CMS]).

There currently are two Medical SAS® Datasets for outpatient care, visit and event.

- **Visit:** One day's occasions of service; and
- **Event:** One ambulatory encounter (coded as DSS Identifier/Clinic Stop).

VHA Decision Support System

The VHA Decision Support System (DSS) is a managerial cost accounting system based on a commercial software named Eclipsys[®]. VHA modified Eclipsys[®] to interact with VistA and other VA national databases to populate the data elements required to allocate VHA costs to VHA products (goods and services provided during patient care). Introduced in 1994, full implementation of the VHA DSS in all facilities was completed in 1999.

The VHA DSS data files comprise a longitudinal, secondary relational database combining selected clinical data and fiscal (cost) data. The DSS provides a mechanism for integrating expenses, workload, and patient utilization. DSS information supports process and performance improvements by measuring quality of care, clinical outcomes, and financial impact. Within a fiscal year, periodic rollups of production data are performed to produce year-to-date non-destructive examinations (NDEs).

DSS Clinical NDEs

- **Laboratory (LAB):** Laboratory test utilization and costs (inpatient and outpatient);
- **Laboratory Results (LAR):** Laboratory test results for a specific list of tests (inpatient and outpatient);
- **Pharmacy (PHA):** Pharmacy prescription utilization and costs (inpatient and outpatient); and
- **Radiology (RAD):** Radiological procedure utilization and costs.

The stability of VHA data sources allows for superior analysis of the continuity of care of patients over multiple years.

US Centers for Medicare & Medicaid Services (CMS) Data

Medicare Inpatient Data

The inpatient claim file contains final action claims data submitted by inpatient hospital providers for reimbursement of facility costs. Some information contained in this file includes diagnosis (International Classification of Diseases, Ninth and Tenth Revision, Clinical Modification [ICD-9-CM and ICD-10-CM] diagnosis code, procedure (ICD-9 and ICD-10 procedure code), diagnosis-related group (DRG), dates of service, reimbursement amount, hospital provider, and beneficiary demographic information. Each observation in this file is at the claim level.

Medicare Outpatient Data

The outpatient claim file contains final action claims data submitted by institutional outpatient providers. Examples of institutional outpatient providers include hospital outpatient departments, rural health clinics, renal dialysis facilities, outpatient rehabilitation facilities, comprehensive outpatient rehabilitation facilities, and community mental health centers. Some information contained in this file includes diagnosis and procedure (ICD-9-CM diagnosis, ICD-9 procedure, ICD-10 diagnosis, ICD-10 procedure, Centers for Medicare and Medicaid Service [CMS] Healthcare Common Procedure Coding System [HCPCS] codes), dates of service, reimbursement amount, outpatient provider number, revenue center codes, and beneficiary demographic information. Each observation in this file is at the claim level.

Medicare Part D Drug Events (PDE) Data

The PDE data contains prescription drug costs and payment data (including out-of-pocket costs [co-payments and deductibles]) that enable CMS to make payments to the plans and otherwise administer Part D benefits. When a beneficiary fills a prescription under Medicare Part D, a prescription drug plan sponsor must submit a summary record to CMS. The PDE data are not the same as individual drug claim transactions but are summary extracts using CMS-defined standard fields.

Skilled Nursing Facility (SNF) Research Identifiable File (RIF)

The SNF file contains final action, fee-for-service (FFS) claims data submitted by SNF providers. This file includes ICD-9-CM and ICD-10-CM diagnosis and procedure codes, dates of service, reimbursement amount, SNF provider number, and beneficiary demographic information.

Home Health Agency (HHA) RIF

The HHA file contains final action, FFS claims submitted by HHA providers. This file includes: number of visits, type of visit (skilled nursing care, home health aides, physical therapy, speech therapy, occupational therapy, and medical social services), diagnosis (ICD-9-CM and ICD-10-CM diagnosis), date of visit, reimbursement amount, HHA provider number, and beneficiary demographic information.

Hospice RIF

The Hospice file contains final action claims submitted by hospice providers. Once a beneficiary elects hospice care, all hospice-related claims will be found in this file, regardless of if the beneficiary is in Medicare FFS or in a Medicare managed care plan. This file includes level of hospice care received (eg, routine home care, inpatient respite care), terminal diagnosis (ICD-9-CM and ICD-10-CM diagnosis), dates of service, reimbursement amounts, hospice provider number, and beneficiary demographic information.

Durable Medical Equipment (DME) RIF

The DME file contains final action, FFS claims submitted by DME suppliers. This file includes diagnosis (ICD-9-CM and ICD-10-CM diagnosis), services provided (CMS Common Procedure Coding System [HCPCS] codes), dates of service, reimbursement amounts, DME provider number, and beneficiary demographic information.

Medicare Carrier File

The Carrier file (also known as the Physician/Supplier Part B claims file) contains final action, FFS claims submitted on a CMS-1500 claim form. Most of the claims are from non-institutional providers, such as physicians, physician assistants, clinical social workers, and nurse practitioners. Claims for other providers, such as free-standing facilities, are also found in the Carrier file. Examples include independent clinical laboratories, ambulance providers and free-standing ambulatory surgical centers. This file includes diagnosis and procedure codes, dates of service, reimbursement amounts, provider numbers, and patient demographic information.

Medicare Denominator File

The denominator file contains demographic and enrollment information of Medicare beneficiaries enrolled or entitled in a given year. It combines Medicare beneficiary entitlement status information from administrative enrollment records with third-party payer information and group health plan (GHP) enrollment information. It is an abbreviated version of the enrollment database (EDB) (selected data elements).

Some information contained in this file includes the beneficiary's unique identifiers, state and county codes, ZIP codes, dates of birth, dates of death, sex, race, age, monthly entitlement indicators (A/B/both), reasons for entitlement, state buy-in indicators, and monthly managed care indicators (yes/no). However, all Medicare files described above can be linked by de-identified patient ID and will be included in the same CMS access request.

Data are collected on an ongoing basis with files constructed annually. It does not contain data on all beneficiaries ever entitled to Medicare. The file contains data only for beneficiaries who were entitled during the year of the data. These data are available annually in May of the current year for the previous year.

9.5. Study Size

All eligible patients available for analysis will be included.

A feasibility analysis was conducted to examine the sample size of patients available in the linked VA and Medicare dataset with diagnosis of NVAf and BMI or body weight reported within ± 6 months of index diagnosis. Enrollment in Medicare Part D was removed as an inclusion criterion during the feasibility analysis as 50% of the study population would be excluded. Many patients in this study population use VA prescription drug benefits due to

cost savings over Medicare Part D. However, we will identify OAC use from Medicare Part D in patients who have this coverage along with VA pharmacy benefits. Approximately 56,000 patients would be included in this study population, with 20,000 included in the apixaban cohort. The VA feasibility study results and hazard ratios (HR) were used to calculate the needed sample size below.

A power calculation was completed for effectiveness outcomes comparing the difference between stroke rates using an alpha of 0.05, power of 80%, an accrual period of 4.5 years (identification period where patients are selected into the study), and a loss of follow-up of 55% for the warfarin cohort and 40% for the apixaban cohort. Using the stroke hazard ratio of 0.63 (from ARISTOPHANES Obesity subgroup²³ and an incidence rate of 1.10 per 100 person-years (from VA-Medicare feasibility analysis conducted in Q1-Q2 2020) in the warfarin group, a Cox proportional hazards analysis of stroke would need 7,945 patients per cohort (1:1 matching).

- **Accrual Period:** 4.5 years (identification period).
- **Loss of follow-up:** 55% for the warfarin cohort and 40% for the apixaban cohort.
- **Alpha:** 0.05.
- **Power:** 80%.

Table 3. Power Calculation

Hazard Ratio (HR) Apixaban vs Warfarin		Incidence Rates for Stroke/SE (per 100 person-years)		Stroke/SE Sample Size		
HR	Source	Rate (warfarin)	Source	Apixaban	Warfarin	Total
OBESITY						
0.63	ARISTOPHANES- Obesity subgroup ²³	1.80	ARISTOPHANES- Obesity subgroup	4,882	4,882	9,764
0.63	ARISTOPHANES- Obesity subgroup	1.10	VA Feasibility	7,945	7,945	15,890
0.76	Sandhu et al ¹⁹	1.28	Sandhu et al	17,769	17,769	35,538
0.76	Sandhu et al	1.10	VA Feasibility	20,646	20,646	41,292
SEVERE OBESITY						
0.72	ARISTOPHANES- Obesity subgroup	1.60	ARISTOPHANES- Obesity subgroup	10,195	10,195	20,390
0.72	ARISTOPHANES- Obesity subgroup	0.87	VA Feasibility	18,640	18,640	37,280
0.39	Hohnloser et al ³²	1.13	Hohnloser et al	2,356	2,356	4,712
0.39	Hohnloser et al	0.87	VA Feasibility	3,055	3,055	6,110

Sandhu et al used BMI ≥ 30 kg/m²; Hohnloser et al used weight > 120 kg

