9.2. Setting

Adult patients prescribed a DOAC or warfarin will be selected between July 1, 2013 and December 31, 2017. Patients will be required to have one or more AF diagnosis claim in any position before or on index date. Patients will be required to have health plan enrollment (Parts A and B) for 6 months prior to the index date to ensure availability of complete patient medical history.

Follow-up Period:

The follow-up period will be defined as the time period between the day after the index date and end of study period (December 31, 2017). Patients will be followed from the day after the index date to 30 days after the date of discontinuation, switch, death, end of study period, or end of continuous medical enrollment (Parts A & B), whichever is earlier.

To assess first stroke/SE event, patients will be censored at first stroke/SE occurring anytime during period on the drug or within 30 days from the last day of days' supply of treatment prescription, 30 days after date of discontinuation, switch, death, end of study or end of continuous medical enrollment (Parts A and B), whichever is earlier.

To assess first MB event, patients will be censored at first major bleeding occurring anytime during period on the drug or within 30 days from the last day of days' supply of treatment prescription, 30 days after date of discontinuation, switch, death, end of study or end of continuous medical enrollment (Parts A and B), whichever is earlier.

For patients with stroke/SE or MB event, net clinical benefit will be assessed by evaluating the first hospital claim for a stroke/SE or MB. The hospital claim can occur anytime during the period of drug use or within 30 days from the last day of supply of treatment prescription.

Other Factors Affecting Censoring During Follow-up

Discontinuation

Discontinuation will be defined as no evidence of index OAC prescription for 30 days from the last day of days' supply of last filled prescription. The date of discontinuation will be the last day of days' supply of last filled prescription. The follow-up will be censored at 30 days after the index drug discontinuation date.

Switch

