9.2.2. Exclusion Criteria

Patients meeting any of the following criteria will not be included in the study:

- Had medical claims indicating a diagnosis or procedure of rheumatic mitral valvular heart disease, heart valve replacement/transplant, venous thromboembolism, or transient AF 6 months prior to or on the index date.
- Had hip/knee replacement surgery within 6 weeks prior to or on the index date.
- Were pregnant during the study period.
- Had an OAC prescription during the 6 months pre-index date.
- Had follow-up time equal to 0 days.
- Had more than one OAC on the index date.

Flag: A flag will be created to evaluate the mechanical heart valve/mitral stenosis during the 6 months prior to or on the index date using narrow definition.

All codes for the selection criteria are detailed in Appendix [Table 4](#).

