INR	VA	International Normalized Ratio Test Results will be identified using Logical Observation Identifiers Names and Codes (LOINC; 34714-6, 38875-1, 46418-0, 52129-4, 5895-7, 5896-5, 61189-7, 6301-6, 72281-9) occurring anytime during the baseline period will be evaluated.
CHADS₂ Score	Both VA and Medicare	CHADS ₂ Score will be calculated according to the points algorithm outlined in Appendix Table 5 .

Variable	Data Source(s)	Operational Definition
CHA2DS₂-VASc Score	Both VA and Medicare	CHA2DS ₂ -VASc score will be calculated according to the points algorithm outlined in Appendix Table 6 .
HAS-BLED Score	Both VA and Medicare	HAS-BLED score will be calculated according to the points algorithm outlined in Appendix Table 7 .
Baseline Medication Use	Both VA and Medicare	A flag will be created for the following medications prescribed during the baseline period: angiotensin-converting enzyme inhibitors/ angiotensin-receptor blockers, aspirin, beta blockers, statins, proton pump inhibitors, H ₂ -receptor antagonists, antiplatelets, nonsteroidal anti-inflammatory drugs, inhibitors of warfarin, inducers of warfarin, dronedarone, digoxin, calcium channel blockers, renin angiotensin system antagonists, glucocorticoids, diuretics, metformin, sulfonylureas, thiazolidinedione, insulin, other diabetes drugs, antiulcer agents, and antidepressants (See Appendix Table 8 for codes).
Bariatric Surgery	Both VA and Medicare	A flag will be created for patients with claims for bariatric surgery (See Appendix Table 9 for codes).
CCI	Both VA and Medicare	Charlson Comorbidity index will be calculated as a continuous variable (See Appendix Table 10 for calculation and codes).
Comorbid Conditions	Both VA and Medicare	The following comorbid conditions will be flagged in baseline: History of stroke/SE, history of bleeding, myocardial infarction, renal disease, liver disease, dyspepsia or stomach discomfort, diabetes, hypertension, congestive heart failure, non-stroke/SE peripheral vascular disease, anemia and coagulation defects , transient ischemic attack, coronary artery disease, peripheral artery disease (See Appendix Table 11 for codes).

Table 2. Clinical and Outcome Variables

Variable	Data Source(s)	Operational Definition

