9.9. Limitations of the Research Methods

A key strength of this study design is that retrospective observational analyses provide a better understanding about the study population in real-world clinical practice and offer complimentary information to controlled clinical trials. Retrospective observational studies also allow the evaluation of patients who are often under-represented in clinical trials, such as those with comorbidities and older adults. Since prescribing patterns in the real world can be complex, retrospective analysis provides a more comprehensive picture of how medications are used by clinicians in routine practice. In addition, the claims databases include all medical and pharmacy claims of patients and allow for longitudinal analysis of a nationally representative sample.

A second key strength of this study design is the linked VA and Medicare databases, which allow us to see a comprehensive patient journey and health resource utilization across two databases. The VHA database includes lab values that will be used to identify obese and severely obese patients as opposed to ICD codes only. Additionally, INR values are available in the VHA data, which will also be evaluated to provide insights into warfarin management.

While claims data are extremely valuable for the efficient and effective examination of health care outcomes, treatment patterns, HCRU, and costs, all claims databases have certain inherent limitations because the claims are collected for administrative purposes and not research. For instance, the presence of a claim for a filled prescription does not indicate that the medication was taken as prescribed or at all. Medications filled over the counter or provided as samples by the physician cannot be observed in the claims data. And the presence of a diagnosis code on a medical claim does not indicate the positive presence of

disease, as the diagnosis code may be incorrectly coded or included as rule-out criteria rather than actual disease.

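### The new-user washout sees only VA and Part D fills, so current anticoagulant users supplied elsewhere can enter either arm as initiators, and no visible analysis tests the effect on the hazard ratio

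*Combined protocol and SAP*

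**What the plan says.** The washout is a single exclusion in section 9.2.2: "Had an OAC prescription during the 6 months pre-index date". It is defined on prescriptions alone. On coverage, section 9.2 states that "Patients will be required to have health plan enrollment (Parts A and B) for 6 months prior to the index date"; neither it nor the inclusion list in 9.2.1 asks for a drug benefit.

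Section 9.5 explains why: "Enrollment in Medicare Part D was removed as an inclusion criterion during the feasibility analysis as 50% of the study population would be excluded". The reason offered is that "Many patients in this study population use VA prescription drug benefits due to" lower cost than under Part D. It adds: "However, we will identify OAC use from Medicare Part D in patients who have this coverage along with VA pharmacy benefits". The expected size follows: "Approximately 56,000 patients would be included in this study population, with 20,000 included in the apixaban cohort".

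Section 9.9 says that "the claims databases include all medical and pharmacy claims of patients". It names over-the-counter drugs and physician samples as unobserved, but not prescriptions filled outside VA and Part D.

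Table 1 in section 9.3 collects INR results from VA laboratory data, "occurring anytime during the baseline period will be evaluated". No inclusion or exclusion criterion uses them. The only sensitivity analysis named in the readable part of section 9.7.2 is propensity score matching.

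**The concern.** Aims 1 and 3 are about patients initiating OACs. A washout delivers initiators only if earlier fills would have been seen. Two routes escape it:

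- A patient without Part D gets an OAC outside VA (for example for cash or through other insurance), then moves the prescription to VA. The first VA fill looks like initiation.
- A patient gains Part D during the period. Fills before coverage are not in the Part D file, so the first covered fill looks like initiation.

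Both routes lead into either arm. A hidden warfarin user may continue on warfarin or change to apixaban, and a hidden apixaban user may continue on apixaban. Established users have come through the early treatment period and may have a different event rate from true initiators, so the hazard ratio could shift. Matching or weighting on recorded covariates cannot correct prior use that is not recorded.

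**Working it through.** **1. The plan's own figure.** Inputs from section 9.5: HR 0.63, warfarin rate 1.10 per 100 person-years, alpha 0.05 (taken as two-sided), power 80%, accrual 4.5 years, loss 55% (warfarin) and 40% (apixaban), read here as annual.

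- Events (Schoenfeld): 4 × (1.960 + 0.842)² / (ln 0.63)² = 147.1, rounded up to 148.
- Event probability with event hazard λ, loss hazard η, uniform accrual over A = 4.5 years and no added follow-up: p = λ/(λ+η) × {1 − [1 − e^(−(λ+η)A)] / [(λ+η)A]}.
- Warfarin: λ = 0.011, η = −ln 0.45 = 0.7985, p = 0.00996. Apixaban: λ = 0.00693, η = −ln 0.60 = 0.5108, p = 0.00820.
- n per cohort = 148 / 0.018155 = 8,152, against 7,945 stated (+2.6%).

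The stated figure reproduces closely and is not in dispute. The same method gives power of about 79% at 7,945 per cohort.

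**2. How many patients rest on VA fills alone.** If the 50% applies to the 56,000, about 28,000 would not have met a Part D criterion. This is an upper limit on the pool in which the first route can operate. It is not a count of hidden users, which the documents do not give.

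**3. Effect on the HR, warfarin arm only.** Assumptions: hidden users are g = 5–30% of warfarin patients without Part D, hence f = 0.5g = 2.5–15% of the warfarin cohort; their event rate is r = 0.5–1.3 times that of true initiators. To first order, observed HR = 0.63 / [1 − f(1 − r)].

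| f | r | Observed HR | n per cohort | Power at 7,945 |
|---|---|---|---|---|
| 0.15 | 0.5 | 0.63/0.925 = 0.681 | 12,231 | 62% |
| 0.10 | 0.7 | 0.63/0.970 = 0.650 | 9,463 | 73% |
| any | 1.0 | 0.630 | 8,152 | 79% |
| 0.15 | 1.3 | 0.63/1.045 = 0.603 | 6,613 | 87% |

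**4. Both arms.** Observed HR = 0.63 × [1 − f_A(1 − r)] / [1 − f_W(1 − r)]. Assume f_W = 5–15%, f_A = 0–15% and r = 0.6–0.8, with r free to differ between arms.

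- Low end: f_A = 0.15 with r = 0.6, f_W = 0.05 with r = 0.8: 0.63 × 0.94/0.99 = 0.598.
- High end: f_A = 0, f_W = 0.15 with r = 0.6: 0.63/0.94 = 0.670.
- Equal contamination with the same r in both arms: 0.63, unchanged.

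**5. What an INR screen would recover.** In the case f = 0.10, r = 0.7 (HR 0.650), a screen that catches a share s of hidden users leaves f(1 − s)/(1 − fs). For s = 25%, 50% and 90% the HR becomes 0.645, 0.640 and 0.632. Its value depends on s, which is unknown.

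**The case against.** The plan's choice is disclosed and reasoned. Many of these patients use VA drug benefits because they are cheaper, Part D fills are used where they exist, and everyone has VA contact: patients are first identified in VA data and need a VA weight or BMI within 6 months of index. All of this shrinks the exposed group, but many is not all, and the remainder is not quantified. Parts of section 9.7.2 are redacted, so a relevant analysis there cannot be ruled out.

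Three stronger readings are tempting, and the documents support none of them.

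- *Half the cohort has an unknown treatment history.* The 50% is the share that would fail a Part D criterion. Only those who also filled an OAC outside VA are misclassified.
- *The bias is toward 1.* This follows only if contamination is confined to, or heavier in, the warfarin arm and established users have lower rates. Step 4 shows a shift either way.
- *Baseline INR would identify these patients, so they should be excluded at entry.* INR comes from VA only, and patients supplied elsewhere may be monitored elsewhere. The baseline window includes the index date, when a true initiator may well be tested. No cut-off has a basis in the documents. Nor is it certain that baseline INR will go unused in adjustment, since the propensity covariate list is left open.

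A Part D restriction was also considered and dropped for sample size. That stands as an argument against an entry criterion, but not against a sensitivity analysis.

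The section 9.9 sentence may be generic wording, and the section does admit some unobserved medication. It still does not fit section 9.5.

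**Conclusion.** The gap is real: followed as written, the plan can index current OAC users as initiators in either the warfarin or the apixaban cohort. Neither the number nor the net direction of bias can be determined from the documents. Under the assumed ranges above, a true HR of 0.63 could appear as roughly 0.60 to 0.68; every contamination share and rate ratio behind that range is an assumption. In most scenarios the shift is modest. This is therefore an inexpensive improvement to the plan. It does not show that the primary comparison is invalid or that the sample size figure is wrong.

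**What to change.** 1. In section 9.7.2, add a sensitivity analysis that repeats the primary apixaban versus warfarin comparison in patients with Part D coverage throughout the 6-month baseline, with propensity weights re-estimated in that subset.
2. Report Part D status by cohort.
3. Add a second sensitivity exclusion, not an eligibility criterion, applied alike in all cohorts: remove patients with evidence of anticoagulant monitoring before the index date (raised or repeated VA INR, or repeated INR-test claims in the Medicare outpatient or Carrier files). Fix the definition before outcomes are examined, and report the number removed by cohort.
4. Correct section 9.9 to say that OAC fills outside VA and active Part D coverage are not observed.

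Cost: two additional runs on data already planned, one table row and one sentence. The Part D subset is about half the cohort; if events halve, the standard error of the log HR grows by √2 ≈ 1.41. If the 50% applies equally, about 10,000 of the 20,000 apixaban patients remain. The feasibility description does not say that these are all obese, so the obese subset may be smaller. Ten thousand exceeds the 7,945 scenario but falls below the 10,195, 17,769, 18,640 and 20,646 scenarios in Table 3, so the subset should be read for consistency of the estimate and not for significance. The monitoring flag will miss some hidden users and remove some true initiators, such as those with a raised INR from another cause or with warfarin started in hospital.
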